11.4.3.3 Substantial Improvement Status for Dropout and Missing data

If a patient fails to provide a urine sample on the last week of the 12-week treatment period OR fails to provide data on two or more of the preceding three weeks, he/she will be considered NOT substantially improved (even if he/she provided negative urines on all other assessment occasions).

Definition of substantial improvement when patient discontinues the study prior to Week 12 in Phase 2. The substantial improvement status for patients who complete all 12 weeks of treatment in Phase 2 will be determined based on whether they satisfy the criteria. For patients who discontinue the study before Week 12 (due to non-compliance, being less than minimally improved after the early treatment, or dropouts) will be considered as NOT substantially improved. (Alternative definitions of substantial improvement status of dropouts will be considered to assess the sensitivity of the inferences about treatment efficacy.)

11.4.4 Hypotheses Testing

11.4.4.1 Primary Hypotheses

Hypothesis 2.1: Among Phase 1 treatment failures on stabilizing BUP/NX treatment, those who received EMM will have higher substantial improvement rate than those who received SMM.

The following model will be used to test this hypothesis:

(1)

$$(2) \quad \text{logit}(Y_{ij}) = \beta_0 + \beta_1 \text{txt}_{ij}$$

Here Y_{ij} is a dichotomous measure indicating whether the j^{th} patient of the i^{th} site meets the criteria for Phase 2 ‘continuous substantial improvement’ or not, with $Y_{ij}=1$ for substantial improvement and $Y_{ij}=0$ for no substantial improvement; txt_{ij} is an indicator variable for treatments, with $\text{txt}_{ij}=1$ for EMM group and $\text{txt}_{ij}=0$ for SMM group. The model parameters will be estimated by GEE (see 13.2.7). Testing this hypothesis is equivalent to testing for significance of \hat{a}_1 .

11.4.4.2 Secondary Hypotheses

Hypothesis 2.2: During the 3 months of treatment, the decrease of probability for positive weekly urines will be faster in the EMM group than in the SMM group.

The course of opiate-free urines over the 12 weeks of the acute treatment will be studied using model (1) below.

(1)

$$(2) \quad \text{logit}(Y_{ijt}) = \beta_0 + \beta_1 \text{txt}_{ij} + \beta_2 t + \beta_{12} t * \text{txt}_{ij}$$

Here Y_{ijt} is a dichotomous measure indicating whether the urine of j^{th} patient in the i^{th} site at time t is opiate-free, with $Y_{ijt}=1$ for opiate-free and $Y_{ijt}=0$ for opiate, t is as in model (1) and t is time, $t=1,2,\dots,12$. Testing the hypothesis is equivalent to testing for significance of \hat{a}_{12} . Presence of a significant interaction between time and treatment would indicate that the reduction of the proportion of opiate positive urines is different for the patients who received the BUP/NX plus EMM than for those in BUP/NX plus SMM group during the active treatment period. If the interaction term is not significant, a model with no interaction term between treatment and time will be fit. In this case, inference about Hypothesis 2.2 will be based on the model with main effects only and testing Hypothesis 2.2 will be equivalent to testing for significance of $\hat{a}_1 = 0$. The presence of a significant treatment effect indicates that EMM group has on average a higher proportion of patients providing opiate-free urines during the treatment period than does the SMM group. GEE will be used to fit this model.

Hypothesis 2.3: EMM will be more effective than SMM with respect to substantial improvement at the end of the follow up period (i.e., at six months post-randomization in Phase 2).

This hypothesis will be tested along the lines of testing the primary Hypothesis 2.1 using model (1).

As a part of this secondary hypothesis, the change in substantial improvement rates during the follow up will be estimated separately for each of the two treatment conditions and overall. The rates will be estimated with point estimates and 95% confidence intervals. Testing will be based on

(1)

$$(2) \quad \text{logit}(Y_{ijt}) = \beta_0 + \beta_1 \text{txt}_{ij} + \beta_2 t + \beta_{12} t * \text{txt}_{ij},$$

where Y_{ijt} is a dichotomous measure indicating whether the j^{th} patient in the i^{th} site at time t meets criteria for substantial improvement, with $Y_{ijt}=1$ for substantial improvement and $Y_{ijt}=0$ for not

substantial improvement, t_{rt} is as in model (2), and t is time, $t=3$ or 6 months post randomization. Testing the hypothesis is equivalent to testing $\hat{a}_{12} = 0$ vs. $\hat{a}_{12} \neq 0$. The presence of a significant interaction between time and treatment would indicate that the effect of EMM versus SMM is different at three months post randomization versus at 6 months post randomization. The hypothesis that overall, the percentage of patients who are substantially improved is the same at three months post-randomization versus at 6 months randomization is a hypothesis about \hat{a}_2 . The model parameters will be estimated and tested by GEE approach.

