3.2 Secondary Objectives

Secondary objectives will determine:

- Subject characteristics that predict likelihood of successful outcomes. Measures included in these analyses will include a) pain status; b) reason for initial use of opioids; c) sociodemographic characteristics (sex, race, age); d) severity of withdrawal symptoms; e) severity of craving; f) presence of current or past heroin use; g) presence of other substance use disorders; h) presence of other psychiatric disorders; i) level of depression; and j) number of previous treatment experiences.
- The percentage of this subject population that responds successfully (as defined below) to a 4-week initial treatment with BUP/NX, either with or without concomitant drug counseling.
- Among subjects who have been unsuccessful in a four-week BUP/NX treatment with taper, the overall percentage of subjects who experience substantial improvement with a 12-week BUP/NX stabilization treatment.
- Whether the probability of having positive urine screens for opioids decreases faster over the 12 weeks of Phase 2 stabilization treatment in the EMM group than in the SMM group (Hypothesis: yes).
- Whether EMM subjects will be more likely than SMM subjects to have substantial improvement at the end of 24 weeks of Phase 2, following the taper of BUP/NX during weeks 13-16 and eight weeks of follow-up (Hypothesis: yes).
- The role of pain in determining or moderating the response to EMM.
- The prevalence and nature of adverse events and serious adverse events in this population with this treatment regimen.

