11.2 General Analytic Strategy

11.2.1 Significance Testing

All hypotheses will be tested by two-sided tests with level of significance $\alpha=0.05$. All exploratory analyses will be reported as such and will be thoroughly described in any publication. In particular, the modeling strategy for identification of predictors of outcome (such as inclusion of multiple covariates and interactions) will be explained in detail to allow adequate assessment of the strength of inferences based on data-driven statistical models.

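### Secondary Hypothesis 2.2 is tested at 0.05 on the treatment-by-time interaction and, if that fails, again at 0.05 on the main effect, so its type I error is about 9.75% and a level difference can stand in for a faster decrease

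*Protocol*

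**What the plan says.** Hypothesis 2.2 (Protocol 11.4.4.2) is that during three months of treatment "the decrease of probability for positive weekly urines will be faster in the EMM group than in the SMM group". The secondary objectives in 3.2 pose the same question: "Whether the probability of having positive urine screens for opioids decreases faster over the 12 weeks of Phase 2 stabilization treatment" in EMM than in SMM.

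The model is a logistic GEE for weekly opiate-free urine, with treatment, time (t = 1 to 12) and their product. The section then gives two tests in sequence:

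- First: "Testing the hypothesis is equivalent to testing for significance of" β12, the treatment-by-time coefficient.
- Then: "If the interaction term is not significant, a model with no interaction term between treatment and time will be fit". In that case "inference about Hypothesis 2.2 will be based on the model with main effects only", and the test of Hypothesis 2.2 becomes the test of β1, the treatment coefficient.

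The protocol interprets a significant β1 as showing that the "EMM group has on average a higher proportion of patients providing opiate-free urines during the treatment period".

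Section 11.2.1 sets the level: "All hypotheses will be tested by two-sided tests with level of significance" 0.05. The protocol neither divides that level between the two tests nor labels the second as exploratory or as a different hypothesis.

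**The concern.** There are two linked problems.

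The first is the error rate. The second test is made only because the first failed, and it uses the full 0.05. That is the reverse of a gatekeeping order, in which a later test is allowed only after an earlier success and the overall level is preserved. Here the hypothesis gets two chances.

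The second is meaning. β12 compares rates of change; β1 in the model without interaction compares average levels. If EMM is better by the same log-odds from Week 1 to Week 12, the two weekly slopes are equal, yet the fallback will tend to be significant and will be booked under a hypothesis that says faster.

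At stake is how a secondary efficacy result is read. Section 11.4.5 ranks evidence from the primary and secondary objectives above exploratory evidence, so a positive Hypothesis 2.2 would carry that extra weight at about twice its stated error rate, and possibly on a quantity other than the one hypothesised.

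**Working it through.** **Inputs from the protocol.** Two-sided level 0.05 (11.2.1); first test β12, fallback test β1 (11.4.4.2); 324 participants in Phase 2 (11.4.3.2); 12 sites (5.2.1), hence 27 per site; 12 weekly urines (11.4.4.2).

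**Two-sided error.** Hypothesis 2.2 is declared if β12 is significant or, failing that, β1 is. If the two tests are independent under the null:

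1 - (1 - 0.05)(1 - 0.05) = 1 - 0.9025 = 0.0975.

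Whatever the dependence, the sum of the two levels is a ceiling: 0.05 + 0.05 = 0.10. The ratio to the stated level is 0.0975 / 0.05 = 1.95.

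**Error in favour of EMM only.** The nominal rate is 0.05 / 2 = 0.025. Under independence the rule gives 0.025 + 0.95 × 0.025 = 0.04875, or about 5%.

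**Are the tests near independent?** The procedure was simulated with no treatment effect, 4,000 trials per setting, using a logit GEE with independence working correlation and robust errors clustered on the participant. Assumed, because the protocol does not give them: participant intercept SD 1.5, participant slope SD 0 to 0.2, site SD 0 to 0.5 (all on the logit scale), and no missing urines.

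| Quantity | Range over four settings |
|---|---|
| β12 test alone | 4.9% to 5.4% |
| β1 test alone | 4.4% to 5.7% |
| Correlation of the two statistics | -0.02 to 0.16 |
| Two-step rule, two-sided | 9.2% to 10.3% |
| Two-step rule, in favour of EMM | 4.4% to 5.3% |

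Each test alone reproduces the protocol's 0.05; the rule that joins them does not. The simulation standard error near 9.75% is √(0.0975 × 0.9025 / 4000) = 0.47 percentage points, so the whole range is compatible with 9.75%, and 10.3% does not contradict the 10% ceiling.

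**Does the fallback answer the stated question?** The protocol's text settles this without a figure: the hypothesis concerns a faster decrease, and the stated interpretation of β1 is a higher average proportion. To show how often the difference could matter, 2,000 trials were run per scenario with participant slope SD 0.1, no site variance and otherwise the same assumptions. The effect sizes are illustrative, not taken from the protocol.

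| True effect (log-odds) | Hypothesis 2.2 declared for EMM through the fallback |
|---|---|
| Constant shift 0.4, equal slopes | 48% |
| Constant shift 0.6, equal slopes | 80% |
| Constant shift 0.8, equal slopes | 92% |
| Constant shift 1.0, equal slopes | 92% |
| Shift 1.0, EMM slope lower by 0.02 per week | 78% |
| Shift 1.0, EMM slope lower by 0.03 per week | 65% |

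Slopes here are set within participants. Averaged over participants they are not exactly parallel, and the interaction test rejected in 6% to 8% of the equal-slope runs. The table counts only declarations made through β1.

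**The case against.** The best defence is that β1 is relevant to the question. Phase 2 arms are randomised, so opioid use before treatment is equal in expectation, and the model starts at t = 1 with no pre-randomisation point. A real gap already present at the first on-treatment urine implies a steeper early fall under EMM, which a linear slope over Weeks 1-12 cannot show. Section 6.2 also frames the outcome more broadly, as EMM's effect on drug use judged by the proportion of negative urines over time. This stands in part. A reader might infer that the main effect is no evidence at all on Hypothesis 2.2; that goes too far. But the protocol does not give β1 the early-fall reading. It calls it an average difference, and with no baseline term the model cannot separate an early fall from a chance imbalance. Two quantities still share one label.

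It can also be said that both steps are prespecified and the meaning of β1 is disclosed. True, but prespecifying two tests at 0.05 does not hold their joint error at 0.05. Dropping a non-significant interaction is ordinary model building, and section 11.4.5 uses it for exploratory questions. Here it defines the test of a named hypothesis.

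The simulations cluster on the participant, whereas section 11.2.7 calls for GEE that handles both site and repeated measurements. In one further setting (site SD 0.5, 3,000 trials) with robust errors clustered on the 12 sites, the rule reached about 15%, but each test alone was then about 8%. That excess is a separate small-cluster matter and is not used here.

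A reader might also infer that Hypothesis 2.3 has the same fault, because the later text says a significant interaction "would indicate that the effect of EMM versus SMM is different at three months post randomization versus at 6 months post randomization", and a lasting benefit with an equal odds ratio at both times would leave that term null. The documents do not support this. Section 11.4.4.2 first says that Hypothesis 2.3 is tested in the manner of Hypothesis 2.1, which is the six-month comparison. The interaction model follows for an added question, the change in improvement rates during follow-up. The wording is loose, but the direct test is not replaced.

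**Conclusion.** The point holds. As written, Hypothesis 2.2 has a two-sided type I error of about 9.75%, with an upper bound of 10%, against the 0.05 in section 11.2.1; for false claims in favour of EMM it is about 5% against 2.5%. The 9.75% rests on near independence of the two statistics, which the simulations support over the assumed variance settings; the bound needs only that each test holds its own level. The excess in favour of EMM is 2 to 3 percentage points.

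The mismatch between a hypothesis about rate and a fallback about level rests on the protocol's text alone. The 48% to 92% figures illustrate it and depend on assumed effect sizes and variances.

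The scope is limited. Primary Hypotheses 1.1 and 2.1 are untouched. A reader might take Hypothesis 2.2 to be a key secondary hypothesis, but the protocol does not rank it above Hypothesis 2.3 or use that term.

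**What to change.** Name one test for Hypothesis 2.2 and delete the rule that removes the interaction when it is not significant. Either choice is workable:

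- If the claim is a faster decrease, test β12 two-sided at 0.05 and let that result stand. Report the average EMM-SMM difference over Weeks 1-12 with a confidence interval, descriptively.
- If the claim of interest is less use overall, reword the hypothesis as an average difference over Weeks 1-12, test that alone at 0.05, and report the difference in slopes descriptively.

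If both are to be tested, make them two separately labelled hypotheses with their own shares of alpha. At 0.025 each, the joint error is 1 - 0.975² = 0.0494 under independence and at most 0.05. Splitting alpha without separate labels would repair the error rate but not the mismatch in meaning.

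The test of Hypothesis 2.3 needs no change. The cost is a wording change in section 11.4.4.2, made before the outcome data are examined, with no effect on visits, data or sample size. The downside is one fewer chance of a significant secondary result or, under a split, less power for each test.

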11.4.3 Statistical considerations

11.4.3.1 Randomization

The randomization to SMM vs. EMM will be within site and will be stratified by whether patients received SMM or EMM in Phase 1. Block randomization will be employed.

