11.4.3.2 Sample size

A total of 324 subjects will be randomized in Phase 2. Participants in Phase 2 are Phase 1 treatment failures. About 50% of patients enrolled in Phase 1 are expected to be eligible, willing, and to actually enroll in Phase 2. The treatment dropout rate in Phase 2 is expected to be lower than that in Phase 1, since participants in Phase 2 have had experience with the study and have agreed to continue, and because dropout from a stabilization dose of BUP/NX is typically lower than that from a tapering dose. In Phase 2 a rate of about 5% treatment dropout per month is expected, resulting in 15% treatment dropout during the three months of treatment and total of 30% treatment dropout for the entire study (10% treatment dropout per month is expected in Phase 1, or about 30% during the three months of Phase 1).

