	0.40	0.55	0.15	1.36
	0.45	0.60	0.15	1.32
	0.50	0.64	0.14	1.29
1.90	0.20	0.32	0.12	1.61
	0.25	0.39	0.14	1.55
	0.30	0.45	0.15	1.50
	0.35	0.51	0.16	1.44
	0.40	0.56	0.16	1.40
	0.45	0.61	0.16	1.35
	0.50	0.66	0.16	1.31
2.00	0.20	0.33	0.13	1.67
	0.25	0.40	0.15	1.60
	0.30	0.46	0.16	1.54
	0.35	0.52	0.17	1.48
	0.40	0.57	0.17	1.43
	0.45	0.62	0.17	1.38
	0.50	0.67	0.17	1.33

Figure 11.2, page 18 shows how the P_{SMM} , odds ratio, total sample size, and correlation within site (ρ) affect the power. Here, the following assumptions were conservatively made:

- The substantial improvement rate in the SMM group is between 30% and 50%.
- The correlation for each pair of responses (substantial improvement) from the same site is about 0.1.
- Between 20 and 30 patients are recruited from each site.

Figure 11.2 Odds Ratios

Top left: Power vs. the correlation for each pair of the substantial improvement rate from the same site (ρ) given site # = 12, sample size per site = 27, $P_{SMM} = 0.30$ and odds ratio = 1.8, 1.9 and 2.0.

Top right: Power vs. P_{SMM} given site # = 12, sample size per site (Phase 2) = 27, $\rho = 0.1$ and odds ratio = 1.8, 1.9 and 2.0.

Bottom left: Total sample size vs. Power given site # = 12, $P_{SMM} = 0.30$, $\rho = 0.1$, and odds ratio = 1.8, 1.9 and 2.0.

This figure conveys at least 80% power to detect an odds ratio of 1.9 between EMM and SMM group or to detect that the difference in substantial improvement rate between two groups is greater than 16% with $324 = 12 \times 27$ total patients enrolled in Phase 2. If the conservative assumption is made that about 50% subjects enrolled in Phase 1 will actually enroll in Phase 2, then the required sample size in Phase 2 is equivalent to a total sample size 648 in Phase 1.

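### Section 11.4.4.2 names a sound six-month test for Hypothesis 2.3, then equates the hypothesis with the treatment-by-time interaction and calls β2 the overall change; both later sentences are wrong as written.

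*Protocol*

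**What the plan says.** All of this is in protocol section 11.4.4.2, under Hypothesis 2.3.

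- The hypothesis: "EMM will be more effective than SMM with respect to substantial improvement at the end of the follow up period", which the section places at six months after Phase 2 randomization.
- The first test: "This hypothesis will be tested along the lines of testing the primary Hypothesis 2.1 using model (1". Equation labels repeat in the text as read, so I identify the model by its link to Hypothesis 2.1 (section 11.4.4.1). That is a logistic GEE with a treatment indicator only, tested through β1.
- A further paragraph, presented as part of the same secondary hypothesis, promises estimates of the change in improvement rates during follow-up, by arm and overall. Its tests come from a model with treatment, time (t = 3 or 6) and their product.
- For that model the section states that testing the hypothesis is the same as testing whether β12 is zero. It adds that a significant interaction "would indicate that the effect of EMM versus SMM is different at three months post randomization versus at 6 months post randomization".
- Finally, "The hypothesis that overall, the percentage of patients who are substantially improved is the same at three months post-randomization versus at 6 months" is said to be a hypothesis about β2.

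Section 11.2.1 makes every test two-sided at 0.05: "All hypotheses will be tested by two-sided tests with level of significance".

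**The concern.** The section attaches two different contrasts to one hypothesis. The first is the EMM versus SMM difference at six months, which is what Hypothesis 2.3 asserts. The second is the difference between the six-month and three-month effects, which is another question. The phrase that equates the hypothesis with a coefficient is the one used to name the deciding test for Hypotheses 2.1 and 2.2. No hypothesis about a changing treatment effect is worded before it. An analyst who follows that sentence literally would judge Hypothesis 2.3 on β12.

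The case is realistic. EMM counseling stops at Week 12, both arms have SMM only in Weeks 13–16, and Weeks 17–24 are follow-up visits only (section 1.2.2.4). Hypothesis 2.3 therefore carries the trial's conclusion on whether the counseling benefit lasts. Read through β12, a fully sustained benefit would look like a null result.

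The β2 sentence raises a second, smaller problem: the coefficient it names does not measure an overall change.

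**Working it through.** **Inputs.** N = 324 in Phase 2 ("A total of 324 subjects will be randomized in Phase 2", section 11.4.3.2). No allocation ratio is given (section 11.4.3.1 says only "Block randomization will be employed"), so I assume 1:1, 162 per arm. The odds ratio of 1.9, the within-site correlation of about 0.1 and the SMM rate of 30% (the low end of 30–50%) are from section 11.5.3. The protocol gives no six-month SMM rate and no within-patient correlation φ between the 3- and 6-month outcomes. I assume 30% (varied from 10% to 50%) and φ from 0 to 0.5.

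**1. The plan's own figure.** Section 11.5.3: "This figure conveys at least 80% power to detect an odds ratio of 1.9 between EMM and SMM group". The EMM rate is 0.30 × 1.9 / (0.70 + 0.30 × 1.9) = 0.449. A two-proportion test with 162 per arm has 79.3% power. Because randomization is within site, a site correlation of 0.1 acts like 162/0.9 = 180 per arm and gives 83.4%. The stated figure reproduces.

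**2. What each coefficient means.** The model is logit P = β0 + β1·txt + β2·t + β12·t·txt, with txt = 1 for EMM.

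- EMM effect at 3 months: β1 + 3β12.
- EMM effect at 6 months: β1 + 6β12.
- Difference between them: 3β12.
- Change from 3 to 6 months in SMM (txt = 0): 3β2. In EMM: 3(β2 + β12).

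So β12 is not the six-month effect. Nor is β1, which is the effect extrapolated to t = 0. And β2 belongs to the SMM arm alone.

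**3. Benefit fully sustained (Hypothesis 2.3 true).** Odds ratio 1.9 at both times, log odds ratio 0.642.

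- β12 = (0.642 − 0.642)/3 = 0, so its test rejects 5% of the time whatever φ is.
- Six-month test: variance = 1/(162 × 0.30 × 0.70) + 1/(162 × 0.449 × 0.551) = 0.0294 + 0.0250 = 0.0543, SE = 0.233, z = 0.642/0.233 = 2.75. Power = Φ(2.75 − 1.96) ≈ 0.79.
- With SMM six-month rates of 10%, 20%, 30% and 50%, power is 48.5%, 69.9%, 78.6% and 80.4%. The β12 test stays at 5%.

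**4. Benefit lost (Hypothesis 2.3 false).** Odds ratio 1.9 at 3 months and 1.0 at 6 months, with 30% in both arms at 6 months.

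- β12 = (0 − 0.642)/3 = −0.214.
- At φ = 0 the variance of 3β12 is 0.0543 + 2 × 0.0294 = 0.1131, SE = 0.336, |z| = 1.91, and the test rejects 48% of the time. At φ = 0.2, 0.3 and 0.5 it rejects 57%, 63% and 77%.
- Over six-month rates of 10–50% the range is 31% to 80%.
- To three decimals every one of these rejections is negative. The six-month test rejects 5%.

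**5. Check by fitted models.** 600 simulated GEE fits per scenario (φ = 0.3, no site effect) gave, for β12 and the six-month contrast respectively, 5.5% and 77% in step 3, and 63% and 5.3% in step 4.

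**6. The β2 sentence.** In step 4 the SMM rate is 30% at both times, so β2 = 0. Yet the rate over both arms falls from (30% + 44.9%)/2 = 37.4% to 30%. A test of β2 would be testing a true null while the overall percentage drops by 7.4 points.

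**The case against.** The strongest reply is that the correct test is already in the text, directly under the hypothesis. The interaction model opens a new paragraph on the change in rates, so the later phrase about testing the hypothesis may refer only to that sub-question and be template wording. The section also interprets β12 correctly and never says that a significant β12 shows EMM superiority at six months. Much of this stands: the first test is sound, and the interpretation sentence is right. What remains is that the sub-question is not worded as a hypothesis, the equivalence sentence does not name it, and nothing states that the first test alone decides.

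On β2, the plan promises change estimates by arm and overall, and for other hypotheses it drops a non-significant interaction, after which β2 would be a common change on the logit scale. That step is not stated here, so the sentence is wrong for the model it refers to.

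Two stronger readings are tempting. A reader might infer from the 48–77% in step 4 that the plan would often claim a six-month EMM benefit that does not exist. It would not: those results are negative, the hypothesis is directional in wording, and the figure is power to detect a real loss of advantage. A reader might also infer an inflated error rate from having two tests at 0.05. That needs a rule under which either test may establish Hypothesis 2.3, and the protocol states no such rule.

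**Conclusion.** The point holds as a wording error in the analysis of one secondary hypothesis. Two sentences of section 11.4.4.2 are wrong: the one equating Hypothesis 2.3 with β12 = 0, and the one assigning the overall change to β2. The cost of following the first literally is a missed sustained benefit: about 5% rejection instead of about 79% at an odds ratio of 1.9.

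The 79% rests on 1:1 allocation, an assumed SMM six-month rate of 30% and no site effect; it falls to about 49% at a rate of 10%. The algebra, and the 5% for β12 under a constant odds ratio, depend on none of these. The calculation also treats the six-month outcome as a separate measurement. Section 11.4.2.2 defines it with the third month of BUP/NX treatment, which needs reconciling as its own point. The primary analysis and the sample size are unaffected.

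**What to change.** Make three wording changes in section 11.4.4.2.

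1. State that Hypothesis 2.3 is decided solely by the EMM versus SMM log odds ratio at six months, from the Hypothesis 2.1 type of model fitted to the six-month outcome. If the joint model is preferred, use β1 + 6β12. Name one of the two.
2. Reword the equivalence sentence so that β12 = 0 is the test of a separate, named sub-question: whether the EMM effect differs between 3 and 6 months. It may remain secondary; there is no need to demote it.
3. Replace the β2 sentence. Test the overall change from the model without the interaction, or average the change over arms. With equal weights on the logit scale the latter is [3β2 + 3(β2 + β12)]/2 = 3β2 + 1.5β12.

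The cost is a few sentences. The data and models are the ones already planned, and Hypothesis 2.3 loses no power.

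### The test named for the overall change from three to six months (beta2) measures the change in the SMM arm only

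*Protocol*

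**What the plan says.** Protocol section 11.4.4.2 adds an analysis of change over follow-up to Hypothesis 2.3: "the change in substantial improvement rates during the follow up will be estimated separately for each of the two treatment conditions and overall". Point estimates and 95% confidence intervals are promised. Testing rests on a GEE logistic model, logit = beta0 + beta1*txt + beta2*t + beta12*t*txt, with t equal to 3 or 6 months.

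The treatment variable is carried over from section 11.4.4.1, where it "is an indicator variable for treatments", with 1 for EMM and 0 for SMM.

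Two coefficients are given a meaning. A significant beta12 "would indicate that the effect of EMM versus SMM is different at three months post randomization versus at 6 months post randomization". For the pooled question the text reads "The hypothesis that overall, the percentage of patients who are substantially improved is the same at three months post-randomization" and continues "versus at 6 months randomization is a hypothesis about" the coefficient with subscript 2, that is beta2. Nothing in this paragraph drops the interaction first, centres the treatment variable or combines beta2 with beta12.

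**The concern.** In a model with an interaction, a main-effect coefficient is the effect at the reference level of the other factor. With SMM coded 0, beta2 is the time slope in SMM. A p-value reported as overall would then describe one arm.

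Three things could follow:
- A fall confined to EMM would not register in this test.
- A change in SMM that EMM offsets would be reported as an overall change.
- Where both arms change alike, beta2 has about the right target but uses only half the patients.

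The p-value could also contradict the overall estimate and interval printed beside it.

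**Working it through.** The protocol gives no figure for this test, so there is none to reproduce. The check is algebra first, then simulation for size.

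**Inputs from the Protocol.** Model and time coding: section 11.4.4.2. Treatment coding: section 11.4.4.1. Two-sided alpha of 0.05: section 11.2.1. Phase 2 sample of 324: section 11.4.3.2.

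**Assumptions.** Allocation 1:1, so 324/2 = 162 per arm. Latent correlation of 0.3 between a patient's two outcomes, complete data at both times, no site effect. All improvement rates below are illustrative.

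**Algebra.**
- SMM (txt = 0): log-odds at t = beta0 + beta2*t, so the change from 3 to 6 months is 3*beta2.
- EMM (txt = 1): log-odds at t = (beta0 + beta1) + (beta2 + beta12)*t, so the change is 3*(beta2 + beta12).
- Equally weighted average of the two log-odds changes: 3*(beta2 + beta12/2).

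Two arms and two times give four cells and four coefficients, so the model is saturated. The estimate of beta2 is then (logit p6 - logit p3)/3 from the SMM data alone. A GEE fit of the stated model to simulated data agreed with that SMM-only formula to about 14 decimals. How time is coded does not change this conclusion; the 0/1 treatment coding produces it.

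**Coefficients per month in three scenarios.**
- (a) SMM 40% to 40%, EMM 55% to 35%. The overall rate goes from (40+55)/2 = 47.5% to (40+35)/2 = 37.5%. beta2 = 0; beta12 = (logit 0.35 - logit 0.55)/3 = (-0.619 - 0.201)/3 = -0.273; beta2 + beta12/2 = -0.137.
- (b) SMM 40% to 30%, EMM 55% to 65%. The overall rate is 47.5% at both times. beta2 = (-0.847 + 0.405)/3 = -0.147; EMM slope = (0.619 - 0.201)/3 = 0.139; average = -0.004.
- (c) SMM 40% to 30%, EMM 55% to 45%. Both arms fall 10 points. beta2 = -0.147; EMM slope = (-0.201 - 0.201)/3 = -0.134; average = -0.141.

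**Rejection rates** (10,000 simulated trials per scenario, Wald tests with robust variance, rounded):

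| Scenario | beta2 | beta2 + beta12/2 | beta12 |
|---|---|---|---|
| (a) only EMM falls | 5% | 81% | about 82% |
| (b) opposite directions, no overall change | 56% | 5% | about 83% |
| (c) both fall 10 points | 55% | 82% | 5% |

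**Which overall contrast.** The sentence concerns a percentage, while beta2 + beta12/2 averages log-odds changes, and the two can disagree. Take SMM 15% to 25% and EMM 50% to 40%. The overall percentage is (15+50)/2 = 32.5% before and (25+40)/2 = 32.5% after. The average log-odds change is (0.636 - 0.405)/2 = 0.115, which is not zero. Here beta2 + beta12/2 rejects in about 11% of trials and the arm-averaged risk difference in about 5%.

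**The case against.** The best defence is that beta2 is meant from a main-effects model, fitted once beta12 proves non-significant. For Hypothesis 2.2, which has the same model form, the protocol says so: "If the interaction term is not significant, a model with no interaction term between treatment and time will be fit". Section 11.4.5 repeats the step for pain, craving and Phase 1 assignment. In a main-effects model beta2 is a common slope from both arms and the power loss in scenario (c) disappears. This is a charitable reading, but the text does not carry it. The step is written out where it is intended and is absent here. For Hypothesis 2.2 it leads to a test of beta1, not beta2. It would also leave the overall test undefined when beta12 is significant, which is when beta2 misleads most.

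The objections to consequence are stronger, and they stand. A reader might infer that the protocol's secondary question about outcome after the taper is compromised. It is not: sections 1.2.2.1 and 3.2 ask whether EMM beats SMM at 24 weeks, and that comparison follows the approach of Hypothesis 2.1 without using beta2. Overall change is an add-on to Hypothesis 2.3.

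A reader might also infer that a loss in EMM would go unseen. It would not: per-arm and overall estimates with 95% intervals are promised. In scenario (a) the interval for the EMM change excludes zero in about 98% of trials, and beta12 flags scenarios (a) and (b) in more than 80%.

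**Conclusion.** The sentence is wrong as written. With the stated coding and model, beta2 tests the SMM change and uses no EMM outcome, so it cannot test an overall change. This follows from algebra and needs no assumption about rates.

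The rejection rates do rest on assumptions: the chosen rates, equal allocation, the 0.3 correlation and no site effect. They show the direction and possible size of the error and do not predict this trial's result. Scenario (c) matters most in practice, because beta12 gives no warning there and about 27 points of power (82% - 55%) are lost for nothing.

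The consequence is limited to one p-value attached to a secondary hypothesis. The primary Phase 2 test, the six-month comparison of EMM with SMM, and the promised estimates and intervals are unaffected. It should be corrected, but it does not threaten the trial's main conclusions.

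**What to change.** Replace the sentence on beta2 in section 11.4.4.2 so that the overall change is tested by the marginal difference in the percentage substantially improved between three and six months, averaged over the two arms and obtained from the same GEE fit. This matches the hypothesis as worded. If an average log-odds change is intended instead, say so and test beta2 + beta12/2; coding treatment as -1/2 and +1/2 makes the time coefficient equal to that contrast. Either way, report 3*beta2 as the SMM log-odds change from three to six months and 3*(beta2 + beta12) as the EMM change.

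The cost is one sentence and one contrast statement. No new data, visits or patients are needed.
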